#### 4.3 Secondary patient-reported outcomes

The following scales will be analyzed for the targeted patient-reported outcomes:

- 1.) Change in perceived social isolation (Likert 1-5 scale: Never, Rarely, Sometimes, Often, Always)
  - a. I feel left out.
  - b. I feel that people barely know me.
  - c. I feel isolated from others.
  - d. I feel that people are around me but not with me.
- 2.) Change in perceived self-efficacy (i.e., "How confident are you that you can stick with healthful foods?" Likert 1-10 scale: ranging from Not Confident to Completely Confident)
  - a. Even if you need a long time to develop necessary routines?
  - b. Even if you have to try several times to make it work?
  - c. Even if you have to rethink your entire way of nutrition?
  - d. Even if you have to make a detailed plan?

3.) Change in perceived caring (i.e., "My current meals help to create a caring environment that helps me heal": Likert 1-5 scale: Strongly Disagree, Disagree, Neither Agree nor Disagree, Agree, Strongly Agree)

All answers to survey questions will be reported at baseline and follow-up in the PRO subpopulation. The change in responses to each survey question will be measured as the difference in score between follow-up and baseline responses. The proportion of participants with a decrease in isolation, increase in self-efficacy, or increase in perceived caring responses from baseline to follow-up will also be reported and compared using chi-squared tests.

A difference-in-differences approach will be used to compare the change in each survey question response by assigned group. The measure of association will be the coefficient (95% CI) for MTMs vs. Usual Care in linear regression models for each change in response adjusted for baseline differences in the PRO subpopulation.

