Participants at the KP Santa Rosa, Santa Clara, Oakland, San Francisco, and San Rafael Medical Centers will be identified daily from EHR data and electronically screened for inclusion criteria using KPNC EHR and associated data systems. After identification, participants will be pre-randomized to intervention or usual care arms using a SAS statistical software randomization program, and a list of initially eligible patients will be uploaded to a KPNC DOR-hosted web application to which only KPNC DOR research staff will have access. After confirming eligibility through manual review of the EHR, KPNC DOR research staff will then call the participant by phone in their hospital room and inquire about their interest in learning about the KP NOURISH Study. If interested, KPNC DOR research staff will review the procedures that the participant would be asked to complete and review verbal consent. Participants providing verbal consent to participate in the study will also be asked for verbal Health Insurance Portability and Accountability Act (HIPAA) Privacy Rule Authorization. Participants providing verbal consent and HIPAA Privacy Rule Authorization will then complete the baseline study visit during the enrollment phone call, which includes questions about sociodemographic characteristics, selected patient reported outcomes, contact information, and ability to receive MTMs (if randomized to receive MTMs). Additionally, following enrollment, KPNC DOR research staff will email the participant thanking them for agreeing to participate in the study and to provide contact information for the study team and for the KPNC Institutional Review Board (IRB) if they have any questions after completing the baseline study visit. This email will also include a study flyer with additional details about their participation in the study. Participants requesting a study mailing will also be mailed the thank you letter and study flyer to their home residence.

After completion of the baseline study visit, KPNC DOR research staff will monitor the participant's discharge status on a daily basis, and upon discharge notify the MTMs service provider (Ceres or POH) to begin delivery service for up to 10 weeks for participants assigned to MTMs alone or and to MTMs with remotely delivered nutritional counseling groups. Participants assigned to the usual care group will be passively

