10.4 Secondary Patient-reported Outcomes

The following scales will be used for targeted patient-reported outcomes:

- 1.) Change in perceived social isolation (Likert 1-5 scale: Never, Rarely, Sometimes, Often, Always)
 - a. I feel left out.
 - b. I feel that people barely know me.
 - c. I feel isolated from others.
 - d. I feel that people are around me but not with me.
- 2.) Change in perceived self-efficacy (i.e., "How confident are you that you can stick with healthful foods?" Likert 1-10 scale: ranging from Not Confident to Completely Confident)
 - a. Even if you need a long time to develop necessary routines?
 - b. Even if you have to try several times to make it work?
 - c. Even if you have to rethink your entire way of nutrition?
 - d. Even if you have to make a detailed plan?
- 3.) Change in perceived caring (i.e., "My current meals help to create a caring environment that helps me heal": Likert 1-5 scale: Strongly Disagree, Disagree, Neither Agree nor Disagree, Agree, Strongly Agree)

Responses to survey questions will be collected at baseline by phone and at the 10week follow-up phone call conducted by KPNC DOR research staff.

11 Supporting Documentation and Operational Considerations

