11.3 Informed Consent Process

Eligible patients will be contacted by phone in their hospital room and asked about their interest in participation in the study during their index hospitalization. Due to Covid-19 restrictions, a waiver of written consent was granted by the KPNC IRB, and all patients interested in participating will be required to provide verbal informed consent. KPNC DOR research staff will explain the purpose of the study, the study procedures, and potential risks and benefits of participation also answer any questions the participant may have before confirming their interest in participating by providing verbal consent.

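### The baseline perceived-caring item is asked in the hospital room with no home anchor, so its change score compares hospital meals with later home or study meals

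*SAP*

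**What the plan says.** **Timing.** Protocol section 6 (Study Design) states that "KPNC DOR research staff will then call the participant by phone in their hospital room". Section 11.3 agrees: "Eligible patients will be contacted by phone in their hospital room". Consenting patients "will then complete the baseline study visit during the enrollment phone call, which includes questions about sociodemographic characteristics, selected patient reported outcomes". Discharge comes later: "After completion of the baseline study visit, KPNC DOR research staff will monitor" for it each day.

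**Item.** Protocol 10.4 and SAP 4.3 give perceived caring as a single statement, "My current meals help to create a caring environment that helps me heal", scored 1 to 5. Neither gives a recall period, asks the patient to think of home, or mentions that the baseline is taken on the ward.

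**Analysis.** In SAP 4.3, "The change in responses to each survey question will be measured as the difference in score between follow-up and baseline responses". For each outcome the SAP also tabulates the share of patients whose answer moved in the favourable direction, and tests it between arms by chi-squared. The measure of association is the arm coefficient from a linear model of the change, adjusted for differences at baseline. The SAP does not say whether the item's own baseline score is one of the adjustment terms. SAP 4.4 repeats these analyses for MTMs alone against MTMs with counseling.

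**The concern.** A change score is interpretable when both measurements concern the same thing. For this item they probably do not. A patient in a hospital bed who is asked about current meals will most naturally think of hospital meals. Ten weeks after discharge, the same words refer to meals at home or study meals.

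Two invented cases show the effect:

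- A usual-care patient whose home diet never alters, but who scores hospital meals 2 and home meals 4, is recorded as +2 and counted as increased.
- A patient who scores hospital meals 5 cannot be counted as increased, whatever the study meals do.

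Aim 3 includes perceived caring. The reported changes and improvement proportions for this item would readily be taken as changes in diet at home. The subtracted score may also add noise to the comparison between arms.

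**Working it through.** **1. The plan's own power figure.** SAP section 2 claims more than 80% power for small differences in patient-reported outcomes, at 1000 v 1000 and 500 v 500, two-sided alpha 0.05. It gives no effect size, SD or baseline-to-follow-up correlation, so the figure cannot be strictly reproduced. With SD = 1, the difference detectable with 80% power is (1.960 + 0.842) × √(2/n):

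- n = 1000: 2.802 × 0.0447 = 0.125 SD
- n = 500: 2.802 × 0.0632 = 0.177 SD

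If small means 0.2 SD (my assumption), power is 99.4% and 88.5%. The claim is plausible for an outcome with SD 1.

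**2. Is the arm comparison biased?** Let the inpatient setting move every baseline answer by b. The mean change moves by −b in each arm, and the difference between arms moves by −b − (−b) = 0. A simulation with 1000 per arm and no meal effect agrees. With b = +0.5 or −0.5 SD, the usual-care mean change is −0.50 or +0.50 SD, and the between-arm difference is 0.00.

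**3. What happens to within-arm results?** This is illustrative and not from the documents. Assume a five-category item with week-10 distribution 8/14/28/32/18%, latent correlation 0.6 between baseline and week 10, and no effect of any meal.

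| Hospital meals relative to home meals | Counted as increased | Mean change (points) | At top score at baseline |
|---|---|---|---|
| 0.5 SD lower | 52% | +0.57 | 8% |
| same | 31% | 0.00 | 18% |
| 0.5 SD higher | 15% | −0.52 | 34% |

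With no meal effect at all, the proportion increased ranges from 15% to 52% according to how hospital food is rated. The lower end depends on the correlation: at correlation 0 with the same upward shift it is 25%.

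**4. Precision.** Let r be the correlation between the two scores, with equal SDs. Relative to the variance of the week-10 score, the variance is:

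- change score: 2(1 − r)
- week-10 score alone: 1
- week-10 score adjusted for baseline: 1 − r²

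Power = Φ(d/√(2·VR/n) − 1.96), where VR is the variance ratio. For d = 0.15 SD and n = 800 per arm (both assumed):

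- Change score, r = 0: VR = 2, SE = √(4/800) = 0.0707, and 0.15/0.0707 − 1.96 = 0.16, so power is 56%.
- Change score, r = 0.3: VR = 1.4, SE = 0.0592, power 72%.
- Week-10 score alone: VR = 1, SE = 0.05, and 3 − 1.96 = 1.04, so power is 85%.
- Adjusted, r = 0.3: VR = 0.91, SE = 0.0477, power 88%.

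At r = 0.5 the change score has VR = 1, the same as the week-10 score alone. Below that it does worse. The adjusted analysis is never worse than either.

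For d = 0.2 SD at the SAP's full sample sizes:

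| r | Change score, 1000 per arm | Change score, 500 per arm | Adjusted, 500 per arm |
|---|---|---|---|
| 0 | 88.5% | 60.9% | 88.5% |
| 0.3 | 96.6% | 76.2% | 91.2% |
| 0.5 | 99.4% | 88.5% | 95.5% |
| 0.7 | 100% | 98.3% | 99.3% |

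**5. Could the planned model already be the adjusted one?** If the model is Y₁₀ − Y₀ = α + β·arm + γ·Y₀, adding Y₀ to both sides gives Y₁₀ = α + β·arm + (γ + 1)·Y₀. The coefficient β is the same. If the item's own baseline score is a covariate, the precision loss in step 4 disappears from the linear model. It remains in the chi-squared comparison.

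**The case against.** The strongest reply is that Hypothesis 3 is a comparison between arms, and steps 2 and 5 show that comparison to be unbiased and possibly already efficient. This stands. A reader might infer that the inpatient baseline biases the estimated effect of MTMs. The documents do not support that for a setting effect shared by both arms. The protection does assume that baseline answers do not depend on allocation. Patients are already randomized when called, and the order of questions in the call is not stated.

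A reader might also infer that the social isolation items record inpatient isolation. That is not established. They use a Never-to-Always frequency scale without a recall period and can be answered about usual life. Nothing here shows a problem with the four self-efficacy items. The clear case is therefore one item of nine, and it would be too strong to say that the changes mainly measure leaving hospital.

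Three further points have force:

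- The documents list the items but not the telephone script, so a spoken lead-in cannot be excluded.
- The ceiling works in both directions: if hospital meals rate lower, there is more room to increase.
- Zero correlation between one person's two ratings is an extreme, and at 1000 per arm a 0.2 SD difference keeps at least 88.5% power.

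The mismatch in what the caring item refers to remains, and neither document addresses it.

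**Conclusion.** The point holds for perceived caring. Its baseline is explicitly taken in hospital, its wording refers to current meals, and nothing in either document ties it to home. Within-arm changes and proportions increased for this item cannot be read as change in diet at home.

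The between-arm difference is not biased by a common setting effect; its exposure is to loss of precision. At 0.15 SD and 800 per arm, change-score power is 56% at correlation 0 and 72% at 0.3, against 85% for the week-10 score alone. The comparison within the MTMs arms is the more exposed: at 500 per arm, power for 0.2 SD falls below the SAP's 80% at correlations of 0 and 0.3. These figures rest on assumed effect sizes, correlations and response distributions, and on the item's own baseline not being among the adjustment terms.

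This is a secondary outcome and does not touch the primary analysis. The correction is cheap enough to be worth making.

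**What to change.** 1. In the baseline script, anchor the caring item to meals eaten at home before this hospital stay.
2. In SAP 4.3, make the main between-arm analysis of perceived caring the week-10 score adjusted for the item's own baseline score. State that the existing adjustment for baseline differences includes that score. Use the same analysis for participants already surveyed with the inpatient wording.
3. For those participants, label within-arm change and the proportion increased as descriptive, not as an effect on home diet.
4. Use one week-10 caring wording in all arms. Protocol 8.3 describes the measure by current meals for usual care but by taking part in the meal program for the MTMs arms, whereas Protocol 10.4 and SAP 4.3 give a single wording. A real difference in wording by arm would not cancel between arms, so the sections should be reconciled.
5. Leave the isolation items as worded.

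The cost is one sentence in the script and a few lines in SAP 4.3, with no extra calls, staff or participants. The downside is some recall error at baseline and, if the change comes after enrollment has begun, two baseline wordings. The adjusted analysis alone needs no script change and no new data.

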Aim 1 (Primary): To determine if MTMs provided for up to 10 weeks after hospital discharge for patients with pre-existing heart failure, diabetes mellitus or chronic kidney disease will reduce the risk of all-cause readmissions at 90 days after discharge.

Hypothesis 1: Patients receiving MTMs will have lower all-cause readmission rates at 90 days compared with patients who are receiving only usual care.

Aim 2 (Secondary): To determine if MTMs provided for up to 10 weeks after hospital discharge for patients with heart failure, diabetes mellitus or chronic kidney disease will reduce the risks of 90-day admissions for heart failure, admissions for diabetes-related complications, all-cause emergency department visits, all-cause death, and a composite of all-cause health care utilization and death.

Hypothesis 2: Patients receiving MTMs will have better clinical outcomes compared with patients who are receiving only usual care.

KP NOURISH Study Protocol Version 1.0

Aim 3 (Secondary): To determine if MTMs provided for up to 10 weeks after hospital discharge for patients with heart failure, diabetes mellitus or chronic kidney disease will experience improved selected patient-reported outcomes (i.e., self-efficacy, social isolation, patient satisfaction, and perceived caring) at 10 weeks post-discharge.

Hypothesis 3: Patients receiving MTMs will have better patient-reported outcomes compared with patients who receiving only usual care.

Aim 4 (Secondary): To determine if MTMs provided for up to 10 weeks with additional remotely delivered nutritional counseling after hospital discharge for patients with heart failure, diabetes mellitus or chronic kidney disease will experience improved all-cause and cause-specific clinical outcomes at 90-days post-discharge as well as selected patient-reported outcomes (i.e., self-efficacy, social isolation, patient satisfaction, and perceived caring) at 10-weeks post-discharge.

Hypothesis 4: Patients receiving MTMs with remotely delivered nutritional counseling will have lower 90-days risks of adverse clinical outcomes and better patient-reported outcomes at 10-weeks post-discharge than patients receiving MTMs alone.

[figure not shown]
6 Study Design

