#### 3.5 Interim analysis

There are no planned interim analyses, and adjustments for multiple comparisons will not be performed.

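### SAP section 4.3 names social isolation and self-efficacy as four-item scales but analyses every question separately, so neither construct has a single estimate or a rule for mixed item results

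*SAP*

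**What the plan says.** Protocol section 5, Aim 3, looks for "improved selected patient-reported outcomes (i.e., self-efficacy, social isolation, patient satisfaction, and perceived caring) at 10 weeks post-discharge". Hypothesis 3 then predicts better patient-reported outcomes with MTMs than with usual care.

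Protocol section 10.4 introduces the instruments with "The following scales will be used for targeted patient-reported outcomes", and SAP section 4.3 with "The following scales will be analyzed for the targeted patient-reported outcomes". Both list the same three entries:

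- social isolation: four statements, each scored 1 to 5;
- self-efficacy: four questions, each scored 1 to 10;
- perceived caring: one statement, scored 1 to 5.

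Neither section gives a sum, mean or other score for the two four-item sets.

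The analysis text in SAP section 4.3 works by question. Change is defined that way: "The change in responses to each survey question will be measured as the difference in score between follow-up and baseline responses". The comparison follows: "A difference-in-differences approach will be used to compare the change in each survey question response by assigned group". The effect measure is the MTMs coefficient with its 95% CI "in linear regression models for each change in response adjusted for baseline differences in the PRO subpopulation". The same section also compares, by chi-squared test, the proportions whose isolation fell, whose self-efficacy rose or whose perceived caring rose.

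SAP section 3.5 states that "adjustments for multiple comparisons will not be performed". SAP section 4.4 repeats all these comparisons between the two MTMs arms.

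**The concern.** Aim 3 asks about constructs, and the SAP answers about questions. Suppose two isolation items favour MTMs and two do not. Nothing in the plan says whether isolation improved, and the emphasis could be chosen after the results are seen.

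The comparison of proportions has the same gap. It is worded by construct, but a participant who improves on one isolation item and worsens on another cannot be classified from the text.

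Two costs follow. More unadjusted comparisons are made than there are constructs. Precision may also be given up, because four answers on one response format are never combined.

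**Working it through.** **The plan's own power figure.** SAP section 2 claims more than 80% power for small differences in continuous patient-reported outcomes, at two-sided 0.05, with 1000 vs 1000 or 500 vs 500. It gives no difference or SD, so the figure cannot be reproduced exactly. It can be checked for plausibility with the smallest difference detectable at 80% power, in SD units, (1.960 + 0.842) × √(2/n):

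- n = 1000 per arm: 2.802 × 0.0447 = 0.125 SD
- n = 500 per arm: 2.802 × 0.0632 = 0.177 SD

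Taking small to mean 0.2 SD (assumption), power is Φ(0.2/√(2/n) − 1.96) = 99.4% at 1000 per arm and 88.5% at 500 per arm. The claim is consistent with the stated sample sizes.

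**Number of estimates.** 4 isolation + 4 self-efficacy + 1 caring = 9 coefficients per comparison. With one score per construct there would be 3.

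**False positives across the regressions.** Assume no effect on any item and each coefficient judged at 0.05.

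- Nine independent tests: 1 − 0.95⁹ = 37.0%
- Nine tests with items correlated within a domain and domains independent (simulation, 400,000 draws): 32.2% at r = 0.5 and 28.2% at r = 0.7; over r = 0.3 to 0.8, 35% to 25%
- Three independent tests: 1 − 0.95³ = 14.3%

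Within one four-item domain, the same simulation gives at least one item below 0.05 in 15.5% (r = 0.5) or 13.0% (r = 0.7) of null cases.

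**Precision of a four-item mean.** Assume equal item SDs, the same shift on every item, and correlation r between the items' change scores. The variance relative to one item is (1 + 3r)/4.

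- r = 0.5: 2.5/4 = 0.625; SD ratio 0.791; standardized effect larger by 1/0.791 − 1 = 26%
- r = 0.7: 3.1/4 = 0.775; SD ratio 0.880; standardized effect larger by 1/0.880 − 1 = 14%

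Power for a shift of 0.1 item SD is Φ(0.1/(s√(2/n)) − 1.96), where s is the SD ratio:

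| n per arm | single item (s = 1) | mean, r = 0.7 | mean, r = 0.5 |
|---|---|---|---|
| 1000 | 60.9% | 71.9% | 80.7% |
| 500 | 35.2% | 43.5% | 51.6% |

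Over r = 0.8 to 0.3, the 1000-per-arm power for the mean runs from 67.9% to 90.1%.

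**Effect of survey completion.** SAP section 3.1 keeps only participants with complete baseline and follow-up surveys. The completion rate is not given. At an assumed 70%, single-item power for 0.2 SD is 96.3% (700 per arm) and 75.4% (350 per arm).

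**The case against.** The item-level plan is prespecified and open about its lack of multiplicity adjustment. These outcomes are secondary, and the declared measure is a coefficient with a confidence interval rather than a pass-or-fail test. For a 0.2 SD effect on MTMs versus usual care, single items have ample power. All of this stands. It limits the precision argument to effects near 0.1 SD and to the 500 vs 500 comparison. It does not supply the missing construct-level estimate.

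Combining items has limits as well. Three scores can disagree just as nine items can, and Hypothesis 3 has no rule for that either; the change gives each construct an answer but not the hypothesis as a whole. Averaging gains precision only if the effect is similar across items.

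Four stronger readings are tempting and are not supported:

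- *Aim 3 names three outcomes.* It names four. Three is the count in Protocol section 10.4 and SAP section 4.3.
- *There are nine further chi-squared tests.* That sentence is worded by construct and does not say whether it applies to each item or each construct. What can be said is that its rule is undefined.
- *The false-positive chance is 37%.* That needs nine independent items, which does not fit with the correlation that makes averaging worthwhile.
- *The SAP's power claim is wrong.* It is not contradicted.

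**Conclusion.** The point holds as a gap in the definition of two secondary outcomes. Social isolation and self-efficacy have four coefficients each, no overall estimate, no rule for mixed results, and a responder comparison that cannot be applied as written. Perceived caring is a single item, so its regression estimate is not affected. This part rests on the text alone.

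The numerical consequences depend on assumptions that the documents do not supply. At a within-domain correlation of 0.5 to 0.7 with independent domains, the chance of at least one false positive is about 28% to 32% for nine regressions, against 14% for three independent outcomes. At the same correlation, with equal item SDs and a similar shift on every item, the standardized effect is 14% to 26% larger for a four-item mean. The power gain at 1000 per arm matters for a 0.1 SD shift (61% to between 72% and 81%) and hardly at all for 0.2 SD. The power figures assume full enrolment with complete surveys. The change should be made, mainly for the missing estimate and only secondarily for precision.

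**What to change.** In SAP section 4.3, make the between-group outcomes:

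1. the mean of the four isolation items;
2. the mean of the four self-efficacy items;
3. the single caring item.

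Model each at follow-up with its own baseline value and medical center as covariates. Center is the randomization stratum in Protocol section 7.4. The scoring change does not depend on this model choice; its purpose is to state exactly which baseline terms enter, which the present wording leaves open.

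Define the proportion improved on these same scores: a lower isolation mean, a higher self-efficacy mean, a higher caring response. State how a survey with a missing item is scored or excluded. Report the individual items descriptively, without tests. Apply the same definitions to the comparison of the two MTMs arms in SAP section 4.4.

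The cost is SAP wording and slightly simpler code, with no new data. The small downside is that an effect confined to one item would be seen only descriptively.

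Patient satisfaction, the fourth outcome in Aim 3, has no between-group analysis. That is a separate gap, which this change does not address.

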### 3 General analysis considerations

### 3.1 Analysis populations

**Primary analysis population**: The primary analysis population will consist of all patients who are randomized and consented to the KP NOURISH study and who survive until hospital discharge, divided into those assigned to MTMs (in addition to Usual Care) and those assigned to receive Usual Care alone. Participants will be analyzed as randomized according to the intention-to-treat principle, regardless of receipt of MTMs.

**Heart failure subpopulation:** The heart failure subpopulation will include all patients in the primary analysis population with pre-existing heart failure as their qualifying medical condition. This population will be analyzed as randomized (MTMs vs. Usual Care) according to the intention-to-treat principle.

**Diabetes subpopulation:** The diabetes subpopulation will include all patients in the primary analysis population with pre-existing diabetes mellitus as their qualifying medical condition. This population will be analyzed as randomized (MTMs vs. Usual Care) according to the intention-to-treat principle.

**Patient reported outcomes subpopulation:** The patient reported outcomes (PRO) subpopulation will include all participants in the primary analysis population with complete baseline and follow-up surveys and excludes participants who died or did not complete the follow-up survey. This population will be analyzed as randomized (MTMs vs. Usual Care) according to the intention to treat principle.

**MTMs subpopulation:** The MTMs subpopulation will include all patients in the primary analysis population who are randomized to either MTMs alone or MTMs with remotely delivered nutritional counseling. This population will be analyzed as randomized (MTMs alone vs MTMs with remotely delivered nutritional counseling) according to the intention-to-treat principle.

**Heart failure MTMs subpopulation:** The heart failure MTMs subpopulation will include all patients with pre-existing heart failure as their qualifying medical condition who are randomized to either MTMs alone or MTMs with remotely delivered nutritional counseling. This population will be analyzed as randomized (MTMs alone vs MTMs with remotely delivered nutritional counseling) according to the intention-to-treat principle.

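### The supplementary chi-squared test of any improvement (SAP 4.3) counts best-at-baseline participants as failures and pools worsening with no change, so it loses power and is hard to interpret

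*SAP*

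**What the plan says.** The items are bounded single questions. Protocol 10.4 lists "Change in perceived social isolation (Likert 1-5 scale: Never, Rarely, Sometimes, Often, Always", self-efficacy on a 1 to 10 scale and perceived caring on a 1 to 5 agreement scale. SAP 4.3 repeats them.

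SAP 4.3 plans three things for each item:

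- **Description.** "All answers to survey questions will be reported at baseline and follow-up in the PRO subpopulation".
- **Binary summary.** A further summary is the "proportion of participants with a decrease in isolation, increase in self-efficacy, or increase in perceived caring responses from baseline to follow-up". Arms are compared on it by a chi-squared test.
- **Main measure.** "The measure of association will be the coefficient (95% CI) for MTMs vs. Usual Care in linear regression models for each change in response". The covariates are unspecified differences at baseline. Change is signed: "The change in responses to each survey question will be measured as the difference in score between follow-up and baseline responses".

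The analysis set in SAP 3.1 "will include all participants in the primary analysis population with complete baseline and follow-up surveys". No rule sets aside, stratifies or separately counts those already at the best score. Neither the inclusion and exclusion criteria (Protocol 7.1 and 7.2) nor the manual review criteria (Protocol 7.5) concern isolation, self-efficacy or food insecurity. SAP 4.4 repeats the 4.3 comparisons between the two meal arms, planned at 500 each.

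**The concern.** The binary summary has two structural weaknesses. First, someone who answers Never to an isolation item, 10 on self-efficacy or Strongly Agree on caring at baseline cannot succeed whatever the meals do, yet counts as a failure in either arm. Second, a participant who moves from Never to Always is scored the same as one who does not change, so an arm that prevents worsening gets no credit.

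At stake are the patient-reported parts of Aims 3 and 4, which are secondary. The percentage improved is the easiest patient-reported result to quote, and it is the only analysis in SAP 4.3 described explicitly as a hypothesis test. A null chi-squared result beside a positive regression coefficient could be read as conflicting evidence when the first is only less sensitive.

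**Working it through.** **1. The plan's own figure.** SAP 2 claims more than 80% power for small differences in continuous patient-reported measures, with 1000 vs 1000 or 500 vs 500 and two-sided 0.05. It gives no difference or SD, so the figure cannot be strictly reproduced, but it is plausible. The difference detectable with 80% power is (1.96 + 0.84) × √(2/n) SD, which is 0.125 SD for n = 1000 and 0.177 SD for n = 500. No power is stated for the chi-squared test.

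**2. Best-score share.** Let c be the share at the best score at baseline, and q1 and q0 the improvement proportions among the rest. The test sees (1 − c)(q1 − q0). Take q1 = 40%, q0 = 30% and 800 completers per arm (assumed):

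| c | Arms compared | Difference | Power |
|---|---|---|---|
| 0 | 40% vs 30% | 10 points | 98.8% |
| 20% | 32% vs 24% | 8 points | 94.6% |
| 40% | 24% vs 18% | 6 points | 83.9% |
| 60% | 16% vs 12% | 4 points | 63.5% |

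**3. Prevented worsening.** Suppose 25% improve in both arms and 25% vs 18% worsen (assumed). The chi-squared test compares 25% with 25% and rejects at its alpha, 5%. Now score worse, same and better as −1, 0 and 1. The mean difference is 0.07. The variances are 0.50 and 0.25 + 0.18 − 0.07² = 0.4251. The standard error at 800 per arm is √(0.9251/800) = 0.034, so z = 0.07/0.034 = 2.06 and power is 54%.

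**4. Simulation of a uniform shift.** Assumptions: 1000 per arm, latent normal baseline and follow-up with correlation 0.6, shift 0.13 SD, a 5-level item, share c at the best score. Entries are the proportion of runs with z > 1.96 in the favourable direction:

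| Analysis | c = 10% | 20% | 40% | 60% |
|---|---|---|---|---|
| Chi-squared, any improvement | 68% | 63% | 49% | 28% |
| Linear change, no covariates | 83% | 82% | 77% | 66% |
| Rank test stratified by baseline level (van Elteren) | 91% | 89% | 88% | 80% |

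Repeat simulations of this scenario put the chi-squared row at 61–69%, 60–63%, 42–49% and 22–28%. Linear regression that also adjusts for the item's baseline score gave 91%, 90%, 86% and 81%, about the same as the stratified rank test. Limiting the chi-squared test to those with room to improve recovers only part of the loss (64%, 65%, 57% and 43% in one run).

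The gap between the second and third rows is the usual gain from adjusting for baseline. On the latent scale the change has variance 2(1 − 0.6) = 0.80, and follow-up given baseline has 1 − 0.6² = 0.64.

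**5. Sensitivity.** With 0.2 SD, correlation 0.5, 800 completers per arm and 5, 20, 40 and 60% at the best score:

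- chi-squared power is 80, 79, 60 and 33%
- linear change gives 95, 95, 92 and 83%
- baseline-adjusted regression gives 99, 99, 98 and 95%

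Here the improved cell carries 50, 49, 43 and 35% of the total movement (more improved plus fewer worsened). Over correlations of 0.3 to 0.7, both scale lengths and control-arm drift of 0 to 0.3 SD, that share runs from 29% to 61%. Simulated type I error of the chi-squared test is 4.8%.

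**The case against.** The strongest reply is that the improved proportion is a companion figure. SAP 4.3 names the linear coefficient as the measure of association, and SAP 2 rests patient-reported power on continuous measures. Signed change counts a move from Never to Always as +4. All answers are reported at both times, so the number at the best score should be visible. On this view, replacing a simple percentage is a matter of efficiency and taste. That stands as a limit on importance: the main patient-reported estimate does not rest on the chi-squared test, and the primary outcome is untouched. It does not repair the test, and the linear model is only a partial answer while its baseline adjustment is left open.

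Three stronger readings are tempting but not supported:

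- **That the test misses most of a real effect.** This depends on the best-score share and the pattern of benefit, and the documents give neither. At 5–20% at the best score, about half the movement is kept in the base case of step 5.
- **That the plan cannot see prevented worsening.** This is true of the chi-squared test only. The signed-change model sees it.
- **That the test is biased.** Chance imbalance in the best-score share is ordinary sampling error, and type I error is sound. Consent and the baseline survey come after allocation (Protocol 6 and 7.4), and only completers are analysed, so selection is possible. That is a separate matter affecting every completer analysis, and conditioning on baseline would remove only part of it.

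**Conclusion.** The point holds for the supplementary chi-squared test. Its definition of success excludes best-at-baseline participants from ever succeeding and ignores worsening. The cost is power and interpretability: about 15 points against the plan's own unadjusted linear change at 10% at the best score (83 − 68), and 38 points at 60% (66 − 28). Conditioning on the item's baseline response adds a further 8 to 14 points over unadjusted change (91 − 83 and 80 − 66).

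These sizes rest on assumed values: a latent normal model, a uniform shift of 0.13 SD, correlation 0.6, full completion at 1000 per arm, and 10–60% at the best score. The structural points, and the complete loss when benefit lies only in prevented worsening, need none of these. The change is worth making because it is cheap, but it concerns secondary outcomes only.

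**What to change.** In SAP 4.3, and for the same comparisons in SAP 4.4:

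- Replace the chi-squared test with a comparison of the follow-up response by arm, conditional on the item's baseline response. Use either a van Elteren test stratified by baseline category or a proportional-odds model with baseline category, and choose one in advance.
- State that the linear model for each item includes that item's baseline score.
- Tabulate improved, unchanged and worsened by arm, with the number at the best baseline score.
- If a percentage improved is kept, give it descriptively, for participants whose baseline score leaves room to improve.

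The cost is a few lines of SAP text and standard SAS procedures, with no new data. The downside is that an odds ratio or rank test is slightly harder to explain than a percentage improved.
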